# 2016N290015\_04 **CONFIDENTIAL** 2019N405280\_00 206246

[figure not shown]
- 3. If the six minute walk(6MW) has been performed in the last 6 months, and participant has been stable on current medications then there is no need to repeat. Historical data will be databased.
- 4. Concomitant medications for the 30 days prior (8 weeks prior for PAH medications) will be reviewed/recorded at screening to evaluate eligibility and changes will be recorded throughout the study.

[figure not shown]
# 3. INTRODUCTION

While considerable advances have been made in treatment, PAH continues to be a serious, life shortening disease. PAH is characterised by impedance to blood flow through the pulmonary vasculature that occurs as a consequence of enhanced pulmonary vasoconstriction, small pulmonary arteriole remodelling, and loss of vessel compliance/distensibility due to perivascular fibrosis [Maron, 2013; Crosswhite, 2014]. Severe pulmonary hypertension leads to right ventricular overload and right-sided heart failure.

GSK2586881 is a purified intravenous formulation of soluble rhACE2 that is being investigated clinically as a potential treatment for PAH. ACE2 is a type I, membrane-bound carboxypeptidase that inactivates Ang II by cleaving it to produce Ang (1-7). Ang II is a key effector peptide of the RAS that can exert deleterious effects on the pulmonary vasculature resulting in vasoconstriction, inflammation, proliferation and structural remodelling, all of which contribute to PAH development (Lipworth, 1994, Cheng, 2005, Schiffrin, 2003). Conversely Ang (1-7) signals through the Mas receptor and has shown vasodilatory, anti-inflammatory and anti-proliferative properties in experimental models (Clarke, 2011). Vasodilation induced by Ang (1-7) has been attributed to the activation of endothelial nitric oxide synthase (eNOS) and the release of nitric oxide (NO) (Sampaio, 2007). The mechanism of action of ACE2 and the downstream consequences are thus distinct from ACE inhibitors and angiotensin receptor blockers (Figure 1).

Systemic and pulmonary Ang II levels have been reported to be increased in patients with idiopathic (I)PAH and are associated with increased pulmonary vascular remodelling (De Man, 2012) while serum ACE2 levels are reported to be decreased in patients with congenital heart disease-associated PAH, and correlate with mPAP (Dai, 2013). The presence of autoantibodies to ACE2 have also been reported in the serum of patients with autoimmune disease with constrictive vasculopathies, PAH or persistent digital ischemia and correlate with reduced ACE2 activity (Takahashi, 2010). Taken together these studies suggest ACE2 activity may be impaired in PAH patients and administration of exogenous ACE2 may be beneficial. This is supported in rodent models of PAH where recombinant ACE2 has proven effective in blocking or treating established PAH in several rodent models, including in BMPR2-mutation related PAH and pulmonary artery banding (Johnson, 2011; Johnson, 2012).

# 3.1. Study Rationale

GSK2586881 is a purified intravenous formulation of soluble rhACE2 that is being investigated as a potential treatment for PAH. GSK2586881 has been tested in healthy subjects (Haschke, 2013) and mechanically ventilated patients with Acute Respiratory Distress Syndrome (ARDS) (GSK study ACE114622; GSK Document Number 2014N217963\_00) and has been shown to be well tolerated with the rapid modulation of RAS peptides. This will be the first GSK study to test the safety and preliminary hemodynamic effects of GSK2586881 in participants with PAH.

# 3.2. Background

PAH is defined as mPAP >25 mmHg at rest and a mean pulmonary wedge pressure of ≤15 mmHg (Galie, 2009). Patients may present with shortness of breath, swelling, fatigue, chest pain, and in advanced cases syncope. Women of childbearing age are most commonly affected, although PAH has been reported in children and older adults. Untreated PAH eventually leads to right sided heart failure and death. PAH is a progressive disease, and mortality and morbidity remain high in spite of recent improvements in therapy.

The development of PAH is associated with connective tissue disease, liver disease, HIV infection, use of appetite suppressants, congenital systemic-to-pulmonary shunts (e.g., atrial septal defect), and portal hypertension. PAH may also occur with no known cause, in which case it is considered primary or idiopathic PAH (IPAH), and as an inherited disease, referred to as heritable PAH (HPAH). IPAH is a devastating disease which if untreated has a median life expectancy of 2.8 years (D'Alonzo, 1991). Outcome for PAH associated with other disorders such as scleroderma is even worse.

At the histologic level, all forms of PAH are characterized by marked structural remodeling of small pulmonary arteries ( $<100\mu$  in diameter); specifically, vascular smooth muscle cell proliferation (medial hyperplasia), intimal fibrosis and hyperplasia, and in situ microthrombosis. In advanced disease, plexiform lesions, likely a disordered attempt at neovascularization, have been identified. These changes in the small

pulmonary arteries lead to narrowing and obliteration of the vessel lumen, increased resistance to blood flow, and increased strain on the right ventricle. The molecular mechanisms underlying this vasculopathy remain poorly understood.

Management strategies for PAH include prevention of microthrombosis using anticoagulants such as warfarin and promoting vasodilation and regression of muscular hypertrophy and intimal fibrosis using endothelin receptor antagonists and phosphodiesterase (PDE) 5 inhibitors (Humbert, 2004). In severe disease or in cases of treatment failure with oral therapy, prostanoids (inhaled, subcutaneous, or intravenous) are used. In selected patients who are not responsive to medical therapy, lung transplant is an option. Despite improvement in medical therapy, only two-thirds of patients are alive 3 years after treatment with the most effective therapy available for PAH, continuous intravenous epoprostenol (Sitbon, 2002). The current therapeutic options remain unsatisfactory, and there remains an urgent need for novel therapies.

A detailed description of the biology, pharmacology, efficacy, and safety of GSK2586881 is provided in the IB (GSK Document Number 2010N108777\_03 and GSK Document Number 2016N300457 00)

## 3.3. Benefit/Risk Assessment

More detailed information about the known and expected benefits and risks and reasonably expected AEs of GSK2586881 may be found in the IB (GSK Document Number 2010N108777 03).

# CONFIDENTIAL

# 3.3.1. Risk Assessment

Potential Risk of Clinical Significance	Summary of Data/Rationale for Risk	Mitigation Strategy	
	Investigational Product (IP) GSK2586881		
Unknown potential for adverse hemodynamic effects in patients with PAH	Pre-Clinical:  Pharmacology studies in rats showed additive reduction in BP when GSK2586881 at single daily dose of 1 mg/kg was given with an angiotensin type 1 receptor blocker or an ACE inhibitor.  Clinical:  No adverse hemodynamic or BP effects noted in the first time in humans (FTIH) healthy volunteer study (APN01-1-01).  No acute adverse hemodynamic effects related to study drug administration or considered significantly different from those expected of patients with ARDS in study ACE114622.	Participants will be monitored including frequent vital signs.  Participants will be excluded if concomitant therapy includes the use of an ACE inhibitor or angiotensin receptor blocker within 14 days prior to dosing.	
Potential Cardiovascular(CV) Effects	Pre-Clinical: In the cynomolgus monkey study, twice daily administration of 10.4 mg/kg (20.8mg/kg/day, highest dose given) for 12 consecutive days resulted in a waveform abnormality in a single female (n=12) which was 6 premature ventricular complexes(PVCs) including an episode of non-sustained ventricular tachycardia (NSVT) consisting of 3 consecutive PVCs (triplet). Timing of the NSVT was 2 to 3 hours following the first daily dose while subsequent PVCs occurred at a	Participants will be monitored including telemetry	

Potential Risk of Clinical Significance	Summary of Data/Rationale for Risk	Mitigation Strategy
	similar time point after the second daily dose. There was no evidence of QT prolongation or anatomical changes in the heart.	
	Clinical: No adverse effects on ECG were seen in the FTIH study (APN01-1-01).	
	In study ACE114622 in ARDS, no clinically significant effects on ECG that were considered related to study drug were observed.	
Potential for Immunogenicity	Clinical: There was no induction of an immune response to rhACE2 in any of the treated subjects up to 28 days after last administration in the FTIH healthy volunteer study (APN01-1-01) or in ARDS patients (ACE114622).	Participants will have routine monitoring of any immunological response that may occur.
Unknown risk of teratogenicity	Pre-Clinical: Reproductive toxicology studies have not yet been performed with GSK2586881. A review of the literature suggests that ACE2 is present in organs of fetal mice late in gestation, and in the placentae of rats, guinea-pigs and humans. Some of the changes noted in the PD and toxicity studies with ACE2 are similar to those reported with an ACE inhibitor. In addition, the older ACE inhibitors are known to be teratogenic in humans.	Pregnancy testing at screening and prior to dosing.  Information on contraception post study will be provided in the informed consent form (ICF).

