# 2. SCHEDULE OF ACTIVITIES (SOA)

Procedure	Screening (up to 28				Trea	ntment Pe	riod				Follow- up Day 7- 14	Follow- up Day 28 ± 3 days	Notes
	days before dosing)	Pre- dose 	0h	0.08h (5 min) 	0.5h	1h	2h	4h	8h	24h		,	
Informed consent	Х												
Genetics consent	Х												Genetics consent is Optional
Inclusion and exclusion criteria	X												Recheck clinical status before randomization and/or 1st dose of study medication
Demography	Х												
Full physical examination including height and weight	Х												
Medical history (includes substance usage and family history of premature CV disease)	х												Substances: drugs, alcohol, tobacco and caffeine
Past and current medical conditions	Х												

	Screening				Trea	atment Pe	riod				Follow- up	Follow- up Day	Notes
Procedure	(up to 28					Day 7- 14	28 ± 3 days						
	days before dosing)	Pre- dose 	0h	0.08h (5 min) 	0.5h	1h	2h	4h	8h	24h		,	
Serum OR urine pregnancy test (WOCBP only)	Х	X									X		
FSH and estradiol test (postmenopausal females only as needed)	Х												
Human Immunodeficiency Virus (HIV), Hepatitis B and C screening	Х												If test performed within 3 months prior to first dose of study treatment, testing at screening is not required
Functional classification	X												
6 Minute Walk Distance	X3												
Admission		Х											Participants may be admitted the day before dosing to enable completion of required pre-dose time point assessments.
Brief physical		Х									Х		
Study Treatment			Х										

Procedure	Screening (up to 28				Trea	Follow- up Day 7- 14	Follow- up Day 28 ± 3 days	Notes					
	days before dosing)	Pre- dose 	0h	0.08h (5 min) 	0.5h	1h	2h	4h	8h	24h		auyo	
Vital Signs	X	X			X	X	X	X	X	X	v		Vital signs will be measured after 5 minutes supine at all time points.
Vitai Signs	^	۸			۸	۸	^	۸	۸	^	X		Triplicate blood pressure (BP) will be taken at screening only.
Pulse Oximetry (SpO 2 )	Х	X			X	Х	Х	X	X	Х	Х		Pulse oximetry will be measured and recorded with each blood pressure assessment
Laboratory assessments (include liver chemistries, haematology panel and coagulation panel)	Х	X								Х	Х		
Urinalysis	Х									Х			
12-lead ECG	Х	Х						X		Х	х		Triplicate will be performed at Screening and Predose

Procedure	Screening (up to 28				Trea	Follow- up Day 7- 14	Follow- up Day 28 ± 3 days	Notes					

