Frocedure	days before dosing)	Pre- dose 	0h	0.08h (5 min) 	0.5h	1h	2h	4h	8h	24h		uays	
Telemetry			←						→				Monitoring to start 30min prior to treatment administration and continue throughout the study until 24h after dosing
Right heart catheter Insertion		←						<del>)</del>					RHC inserted prior to dose and removed after the 4h hemodynamic measurement
Blood sample for biomarkers of disease activity		Х					Х	Х		Х			
Blood sample for Nitric Oxide		Х					Х	Х		Х			
Blood sample for PK		Х		Х	Х	Х	Х	Χ	Х	Х			
Blood sample for immunogenicity		X									Х	Х	Additional visits may be required. (see Section 9.7 for details).

Procedure	Screening (up to 28				Trea	ntment Pe	riod				Follow- up Day 7- 14	Follow- up Day 28 ± 3 days	Notes
	days before dosing)	Pre- dose 	0h	0.08h (5 min) 	0.5h	1h	2h	4h	8h	24h		auyo	
Blood sample for renin- angiotensin system biomarkers		X		х	Х	Х	X	х	X	х	х		
Blood sample for pulmonary wedge RAS biomarkers		Х				Х	Х	Х					
Hemodynamic measurements		Х				Х	х	х					
Genetic sample		Х											Can be taken any time after consent has been signed. Only required once and is optional.
Discharge										Х			
AE review		←==	======			==>	Х						
SAE review	Х	←==	←										
Concomitant medication review 	Х	Х									Х		

Pre-dose measurements may be taken any time after admission up until dosing.
 Procedures will be completed immediately after dosing has completed.

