#### 5.5. Dose Justification

GSK2586881 has been studied in 21 healthy subjects as single, intravenous doses over 30 minutes from 0.1 mg/kg to 1.2 mg/kg, and in repeated daily doses for up to six days of 0.4 mg/kg once a day. In addition, ARDS patients have received four doses of GSK2586881: 0.1 mg/kg, 0.2 mg.kg, 0.4 mg/kg and 0.8 mg/kg over a 24 hour period (n=5) or 0.4 mg/kg BID for 3 days (n=19).

A preliminary population PK model for GSK2586881 has been derived from data obtained in healthy subjects and ARDS patients and showed that the systemic PK profile was adequately described by a two-compartment first order elimination model and that the PK profile was independent of population (healthy subjects or ARDS patients). Decreases in Ang II levels occurred rapidly after GSK2586881 administration with Ang II concentrations maximally or near maximally reduced at the first sampling time of 5 minutes post-dose; consistent with maximal plasma concentrations of GSK2586881. The PK/PD response (the relationship between ACE2 and Ang II) in healthy subjects and ARDS patients appeared to be best described with a single direct Emax model after accounting for differences in baseline Ang II concentrations between healthy subjects and ARDS patients. The observation of no significant delay between GSK2586881 concentration and effect is in line with its mechanism of action as an enzyme on a substrate.

Based on the preliminary population PK/PD model described above, it is predicted that following a single dose of ≥0.2 mg/kg, Ang II concentrations will on average be reduced below participant baseline levels for at least 24 hours post-dose (assuming Ang II levels in PAH participants is consistent with levels reported in ARDS participants in GSK study ACE114622 (GSK Document Number 2014N217963\_00). The 0.8mg/kg dose has been selected to investigate the safety and tolerability dose range for GSK2586881 in this patient population.

In an investigator-sponsored study (NCT01884051) GSK2586881 has been studied in 3 PAH patients as a single, intravenous dose at 0.2 mg/kg, and in 2 patients at 0.4mg/kg. There were no SAEs and no dose limiting toxicities were observed.

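### No blood pressure or SpO2 reading is scheduled between pre-dose and 0.5 h, although blood is already drawn straight after the 3–5 minute push; adding one would be a cheap, minor improvement

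*Protocol*

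**What the plan says.** Section 3.3.1 (Risk Assessment) lists an unknown potential for adverse hemodynamic effects in PAH. Its mitigation is "Participants will be monitored including frequent vital signs", together with exclusion of recent ACE inhibitor or angiotensin receptor blocker use.

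Section 2 (Schedule of Activities) sets the times:

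- **Vital signs:** pre-dose, then 0.5, 1, 2, 4, 8 and 24 h, with the note "Vital signs will be measured after 5 minutes supine at all time points". The 0 h and 0.08 h cells are blank.
- **SpO2:** the same times, with the note "Pulse oximetry will be measured and recorded with each blood pressure assessment".
- **PK and systemic RAS blood:** pre-dose, 0.08, 0.5, 1, 2, 4, 8 and 24 h. Footnote 2 says of the 0.08 h column: "Procedures will be completed immediately after dosing has completed".
- **Catheter hemodynamics:** pre-dose, 1, 2 and 4 h. The catheter note reads "RHC inserted prior to dose and removed after the 4h hemodynamic measurement".

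Section 7.1 gives the dose as an IV push over 3–5 minutes. Section 7.2 gives as one example of a dose-limiting toxicity (DLT) a mean arterial pressure below 60 mmHg or a 25% fall in systolic pressure. One DLT at least possibly related to drug halts further dosing pending a safety review, and two in a cohort mean the maximum tolerated dose has been exceeded.

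**The concern.** The one post-dose sampling time without a blood pressure is the earliest. Section 5.5 reports "Ang II concentrations maximally or near maximally reduced at the first sampling time of 5 minutes post-dose", in line with peak plasma concentration, and finds no significant delay between concentration and effect. If blood pressure also responds early, the response would fall in the stretch where nothing is scheduled. The protocol does not say when blood pressure would change, so that step is an inference.

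At stake is what the escalation review sees. A fall that crosses the example hypotension threshold, causes no symptoms and has gone by 0.5 h would not have to be recorded. With cohorts as small as 4 and rules that act on one or two events, a single unrecorded event could matter.

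**Working it through.** The protocol states no figure on this point, and its sample size is not statistically based (Section 10.1). The check is a reading of the Schedule of Activities plus simple arithmetic.

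**Scheduled post-dose times within 24 h (Section 2)**

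| Item | 0.08 h | 0.5 h | 1 h | 2 h | 4 h | 8 h | 24 h | Count |
|---|---|---|---|---|---|---|---|---|
| PK and systemic RAS blood | yes | yes | yes | yes | yes | yes | yes | 7 |
| Vital signs and SpO2 | no | yes | yes | yes | yes | yes | yes | 6 |
| Catheter hemodynamics | no | no | yes | yes | yes | no | no | 3 |

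The blanks at 0.08 h do not look like a fault of text extraction: the vital-sign and SpO2 rows agree with each other, and the PK and RAS rows are filled in that column.

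**Length of the gap**

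- If 0 h is the start of the push, the first reading comes 30 − 5 = 25 to 30 − 3 = 27 minutes after the push ends. If 0 h is the end of the push, it comes 30 minutes after.
- As a share of the first day: 30 / 1440 = 2.1%. This measures time only, not risk.
- With a reading at 0.08 h (5 min), the remaining interval to 0.5 h is 30 − 5 = 25 minutes. A further reading at 0.25 h would split it into 15 − 5 = 10 and 30 − 15 = 15 minutes.

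**Does anything else fill the gap?**

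- *Catheter:* the first post-dose set is at 1 h, and the variables in Section 9.1.1 include no systemic pressure.
- *Telemetry:* it runs throughout, but Section 9.5.5 specifies no blood pressure and databases only telemetry findings linked to AEs or SAEs.
- *Monitoring under site procedures:* Section 3.3.1 offers this as mitigation for catheterization, with no blood pressure time and no recording rule.
- *AE collection:* Section 9.2.1 starts it at treatment, but a silent fall has to be measured before it can be reported.

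**How far the earlier data reach**

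Section 5.5 says that the healthy subjects received single doses over 30 minutes, against a 3–5 minute push here. Their clean blood pressure record therefore does not directly address the minutes after a push. Section 5.5 gives no infusion rate for the ARDS patients or for the five earlier PAH patients.

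**Margin to the example threshold**

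Inclusion criterion 7 asks only for a mean pressure above 60 mmHg. Exclusion criterion 1 draws its line at 90 systolic and 50 diastolic. Assuming the usual one-third approximation, mean pressure at 90/50 is 50 + (90 − 50)/3 ≈ 63 mmHg, about 3 mmHg above the example DLT limit.

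**Readings added**

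- One reading at 0.08 h: 4 cohorts × 4 = 16, up to the maximum of 27 completers. Each replaced participant adds one.
- With 0.25 h as well: 2 × 16 = 32 to 2 × 27 = 54.
- Scheduled post-dose readings within 24 h: now 6 × 16 = 96 to 6 × 27 = 162; with 0.08 h, 7 × 16 = 112 to 7 × 27 = 189.

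**The case against.** The strongest reply is that nothing here is wrong. Six readings in 24 h meet the promise in the risk table, and other procedures, such as the ECG, also have no 0.08 h mark. That stands, and it is why this is a suggestion and not an error.

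Second, the missed event needs several things at once: it must be early, silent, beyond the threshold and gone by 0.5 h. Section 5.5 predicts that from 0.2 mg/kg upward Ang II stays below baseline on average for at least 24 h, assuming ARDS-like levels, so a fall driven by Ang II should still be visible at 0.5 h. Only the lowest dose, 0.1 mg/kg, lies outside that prediction. Earlier experience also reassures. For ARDS, Section 3.3.1 reports "No acute adverse hemodynamic effects related to study drug administration or considered significantly different from those expected of patients with ARDS in study ACE114622"; it reports no adverse blood pressure effect in healthy volunteers; and the five earlier PAH patients had no SAE or DLT. Dosing is medically supervised. All this stands, and it makes the likelihood look low.

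Third, a DLT depends on how severe or lasting the toxicity is, so a brief silent dip might not count. True, but the review can exercise that judgement only on values it has.

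Fourth, the new reading would not follow the measurement standard. Sections 2 and 9.5.2 ask for 5 minutes of rest, and Section 9.5.2 wants it quiet, whereas at 0.08 h the participant has just been injected and is having blood drawn. A low value taken then could raise a DLT question and pause dosing. This is a real cost. It calls for a note in the schedule, but it does not outweigh having a value at the expected peak.

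**Conclusion.** The point holds as a minor improvement. The schedule requires no recorded blood pressure or SpO2 between pre-dose and 0.5 h: 1 of 7 post-dose sampling times, and a gap of 25 to 30 minutes after the push that includes the expected concentration peak. No text elsewhere in the protocol requires a recorded systemic pressure in that window.

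No probability of a missed event is claimed, because the documents give no rate for short-lived falls. The conclusion rests on two assumptions: that blood pressure could respond at about the time of peak concentration, and that site procedures do not already guarantee a recorded reading that reaches the review. If sites do take and report one, the change only writes down existing practice.

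**What to change.** In the Schedule of Activities, mark vital signs at the existing 0.08 h column; SpO2 follows under its own note. Add a short note that the participant lies supine from before the push, that the automated device is used, and that the 5-minute rest may overlap the push. Record the values on the CRF and include them in the dose-escalation safety review, which should bear in mind that the rest was not undisturbed. A reading at 0.25 h is optional and would help show whether a low value persists.

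The cost is one mark and one note, with 16 to 27 extra cuff and SpO2 readings over the study (32 to 54 with 0.25 h). Blood is already drawn at 0.08 h, so no new visit or staff is needed. The drawback is a cuff reading next to the PK and RAS draws.

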# CONFIDENTIAL

Potential Risk of Clinical Significance	Summary of Data/Rationale for Risk	Mitigation Strategy
Potential for Rash	Clinical: In study ACE114622, rash was reported more frequently in subjects receiving GSK2586881, although only one event was considered drug-related.	Participants will be monitored for rash in the clinical trials.
	Study Procedures	
Pulmonary arterial catheterization (PAC)	More common risks of PAC placement include: bruising at the site of the PAC insertion, excessive bleeding, vein injury or tear or pneumothorax. Less common complications include: thrombosis, infection, hypotension, arrhythmia, cardiac tamponade or pulmonary artery rupture.	Insertion of catheter performed by experienced physicians, continuous monitoring of participants during procedure per site standard operating procedures (SOPs).
Exposure to ionzing radiation	Catheter placement may be confirmed by chest X-ray or fluoroscopy, as clinically indicated. Both chest X-ray and fluoroscopy are assumed to increase the risk of cancer or heritable effects due to radiation exposure. Radiation exposure from chest X-ray is minimal (0.02mSv). Radiation exposure from fluoroscopy used to confirm placement of the catheter is dependent on the equipment and duration of the procedure. The dose will typically be around 2mSv but may range from 2-5mSv. The additional risk of developing a fatal malignancy (cancer) as a result of these exposures has been estimated as between 1 in 10,000 and 1 in 2000 for an adult in normal health.	Negative pregnancy testing prior to procedure. Minimize fluoroscopy time; lead shielding per site SOPs. Maximum exposure will not exceed 10mSv to confirm placement of the catheter.

